To be specific, young and middle-aged CRC patients (18 - 60 years) experienced higher occurrence rates for almost 50% of the symptoms due to their receipt of more intensive, shorter-cycle chemotherapy regimens, lower baseline functional status, and the emergence of unique chemotherapy-toxicity symptom clusters (Morse et al., 2024). Young and middle-aged cancer survivors (age < 60) with two or more comorbid conditions are more likely to have more and severe physical or emotional symptom (Jeon et al., 2019). In addition, compared to older patients, young and middle-aged patients are more likely to be exposed to complex social factors, such as financial stress and social isolation, following a cancer diagnosis. Specifically, the treatment of cancer will affect their work and thus cause severe economic toxicity (Alsakarneh et al., 2024; Ghazal et al., 2023); Social isolation is more common in young and middle-aged patients because cancer affects their careers and relationship (Fletcher et al., 2024; Khoo et al., 2022); For patients of childbearing age, the impact of cancer on their fertility is an even more specific negative factor in leading to a bad outcome (Baronas et al., 2024; Patel & Ahnen, 2018). Specifically for young and middle-aged CRC patients in China, studies have shown that they struggle to rebuild their social support networks and to access and screen

relevant health information, so that their health needs span the entire disease journey (Yajuan et al., 2024). In addition, CRC survivors frequently experience anxiety about treatment outcomes, future prognosis, and long-term survival, with emotional or psychological support and reassurance, information about managing illness and side effects, fear of cancer recurrence, and help with sexuality problems identified as their top unmet needs (Luo et al., 2024; Ng et al., 2019). Therefore, under such complex and numerous psychological and social challenges, resilience plays an important role in helping patients to cope well with the difficulties associated with cancer. Currently, few programs exist to enhance resilience in young and middle-aged colorectal cancer survivors after they finish primary treatment, even though they have distinct challenges. Developing tailored resilience-building interventions for this group will not only support their immediate well-being but also help them maintain better health as they age, thereby meeting their long-term medical and care needs.

Resilience is often described as an outcome, more specifically, an individual response to a difficult life-situation and a psychosocial outcome of growth, is crucial for CRC patients (Deshields et al., 2016; Southwick et al., 2014). Effectively managing emotions is a vital aspect of emotional well-being, and resilience underpins the ability of young and middle-aged CRC survivors to maintain their mental health and overall quality of life. According to the affect-regulation framework of psychological resilience, resilience has come from two major sources: the stress and coping approach and the emotion and emotion-regulation approach, guiding the development of most resilience-enhancing interventions (Compas et al., 2017; Lazarus, 2000; Troy et al., 2023). Within the transactional stress and coping framework, stressors that exceed individuals' coping capacities necessitate cognitive and behavioral adaptations to reestablish equilibrium. For those with low resilience, these adaptations require complex cognitive restructuring under high-stress conditions, which can impose undue psychological burden (Troy et al., 2023; Xiang et al., 2025). As mentioned, young and middle-aged colorectal cancer survivors already contend with significant psychosocial challenges, renders them particularly vulnerable to this burden. Consequently, mandating targeted cognitive or behavioral adaptations before resilience is bolstered may exacerbate distress rather than alleviate it. Yet emotions motivate cognition and behaviour, influencing adaptive or maladaptive pathways without being resistant and overburdened for patients with low resilience and high emotional burden (Barrett et al., 2007; Izard et al., 2002; Leichsenring, 2001).

Regarding the important role of adaptive and moderate emotion regulation in enhancing resilience. Existing emotional interventions have been developed to manage negative emotions

and improve resilience in cancer patients. A recent systematic review and network meta-analysis identified attention and interpretation therapy and positive psychology as effective emotional approaches for improving resilience (Ding et al., 2024). The two approaches enhance the resilience of cancer patients by, respectively, providing psychologically relevant positive coping strategies to help cancer patients better adapt to their environment (Cerezo et al., 2014), and diverting attention from cancer to avoid negative emotions (Lin et al., 2020). Following this review, a subsequent study developed the Managing Cancer and Living Meaningfully (CALM) intervention that incorporates emotional strategies. This intervention combines virtual reality (VR) technology to improve the resilience of breast cancer patients by providing guidance and emotional support for symptom management and facilitating emotional expression. However, these interventions provide patients with general strategies for emotion regulation, but do not focus on improving the patient's ability to effectively utilize these strategies, which is a key factor in effectively applying these emotional strategies to improve resilience (Kashdan et al., 2015).

Emotional granularity, or the ability to differentiate and label emotional experiences with precision, plays a crucial role in emotion regulation and resilience (Barrett, 2006; Tan et al., 2022). According to Barrett's Conceptual Act Theory (CAT), emotions are constructed through the integration of core affect and conceptual knowledge (Barrett, 2006). This allows individuals to recognize, differentiate, and interpret their emotional experiences, leading to more effective emotional responses (Gross, 2015). Previous study show that individuals with low emotional granularity exhibit reduced effectiveness of emotion regulation strategies, resulting in increased negative affect, whereas those with high differentiation manage emotional intensity more successfully and demonstrate greater psychological flexibility (Kalokerinos et al., 2019). This precision also fosters more effective emotional regulation, a key component of resilience in the face of adversity, by enabling patients to identify specific emotional experiences, which allows them to apply more targeted emotional strategies (Deshields et al., 2016; Erbas et al., 2022; Gross, 2015).

In summary, for young and middle-aged CRC patients, there are more key emotional and social factors challenges whether they arise from the disease, treatment outcomes, family responsibilities, career disruption or socialization. In this context, improving patient resilience can help them adapt to these stressors, maintain mental health, and recover from emotional setbacks. Although emotional methods have been available in existing research as effective and adaptive interventions to improve patient resilience (Casellas-Grau et al., 2014; Ding et al.,

2024; Polizzi & Lynn, 2021), so far there are no studies targeting on what and how effective of these emotional strategies adopted by the patients. Emotional granularity contributes to this process by enabling patients to recognize specific emotional experiences, which in turn enables them to more effectively apply targeted emotion regulation strategies. Therefore, we hypothesized that by increasing emotional granularity in young and middle-aged CRC patients, patients could use emotion regulation strategies more effectively in the face of the emotional complexity of the cancer journey, thereby improving patient resilience and promoting overall health as well as quality of survival.

Methods

1. Aim

To clarify the relationship between emotional granularity and resilience, explore young and middle-aged CRC patients' emotional challenges and investigate how resilient patients leverage emotional granularity to support adaptive emotion regulation strategies, as well as examine patients' perspectives on interventions development.

2. Study design

This study was designed as a sequential mixed-method study that first collects and analyses quantitative data and then qualitative data to explain or generalize quantitative data (Creswell & Clark, 2017). The study will include two-phases, including quantitative phase to explore the association among emotional granularity, emotional regulation and reliance in young and middle-aged CRC survivors, then a qualitative phase to further elucidate the findings from the quantitative phase and delve deeper into the emotional challenges faced by young and middle-aged CRC patients, as well as their perspectives on AI-integrated emotional interventions.

3. Participants

The research design for the first quantitative phase is a cross-sectional, anonymous survey. young and middle-aged CRC patients will be recruited consecutively from Chinese medical institutions in Suzhou, Jiangsu Province. Potentially eligible participants will be identified from electronic medical records in accordance with the hospital's strict data security policies. The inclusion criteria are (1) young and middle-aged adult patients (age in the range of 18-60 years); (2) patients diagnosed with CRC; (3) patients have completed primary treatments (e.g., surgery, chemotherapy, and/or radiotherapy) without experiencing a recurrence of CRC; and (4) patients

able to use a smartphone and agree to participate in the study. The exclusion criteria are (1) patients who have not been informed of their cancer diagnosis due to family decision to withhold information; and (2) patients suffering from severe conditions that may affect participation or assessment, such as significant cognitive impairment, psychiatric disorders, or communication disorder. Before the survey, patients are required to sign an informed consent form. Regarding the sample size, Monte Carlo simulation for mediation analysis will be used (Donnelly et al., 2023; Fritz & MacKinnon, 2007). We will begin by specifying our population parameters based on the smallest effect size of interest (SESOI). In our mediation model, the following paths were defined: Path a is the effect of emotional granularity on emotional regulation. Path b is the effect of emotional coping on resilience (while controlling for emotional granularity). Path c is the direct effect of emotional granularity on resilience after accounting for the mediator (Figure 4). standardize example value of $a=0.5$, $b=0.4$ (Donnelly et al., 2023). 200 participants will reliably ensure at least 80% power. Moreover, considering a 15% attrition rate, the sample size should be 236 at least.

For subsequent qualitative phase, semi-structured qualitative individual interviews will be used to collect in-depth insights from young and middle-aged CRC survivors from quantitative part. According to the sample size requirements for interview in qualitative research in social sciences (Bekele & Ago, 2022), 20-25 participants will be selected based on quartiles of CDRS scores in the quantitative phase to explore common perspectives as well as emotional strategies employed by patients in different score bands to ensure that the qualitative interviews include a diverse range of perspectives, and will capture variations in emotional coping strategies and resilience.

[figure not shown]

Figure 4 Path assumption

4. Data collection for quantitative phase

Nurses or post graduate nursing students will be recruited as research assistants to support participant screening, data collection, and follow-up assessments. They will be responsible for identifying eligible participants and explaining the study procedures. After providing informed consent, participants will complete the questionnaires. For participants who have difficulty reading the written questions, the research assistants will read the questions and options verbatim without adding any interpretation. After the questionnaires are submitted, the research assistants will check them for completeness. See appendix 1 for the questionnaire used for the survey. Measurement tools used for the survey will include the following.

General Information Questionnaire

The general information questionnaire will be self-designed after literature review. The questionnaire includes age, sex, nationality, marital status, education, occupation, religious beliefs, monthly per capita household income, payment method of medical expenses, and other diseases. CRC family history, cancer types, metastasis, treatments received, stoma-related information.

The Chinese version of Range and Differentiation of Emotional Experience Scale (RDEES)

Emotional granularity, also referred to as emotional differentiation or emotional complexity will be evaluated by RDEES. It was developed by American scholars Kang and Shaver in 2004 (Kang & Shaver, 2004). The original English version comprises 14 items across two subscales: Range and Differentiation. In 2013, Chinese researchers deleted 3 items from the original scale after translation and cultural adjustment, and finally obtained the Chinese version of the RDESS, which consists of 11 items, including the range of emotional experience and emotional experience differentiation dimensions, with a Cronbach's alpha coefficient of 0.82 (Wang H. et al., 2015).

The Chinese Version of Difficulties in Emotion Regulation Scale (DERS)

The version of the scale was developed in 2004 with 36 items to assess multidimensional challenges in emotion regulation, including nonacceptance of emotions, difficulties engaging in goal-directed behavior, impulse control issues, lack of emotional awareness, limited access to regulation strategies, and lack of emotional clarity (Gratz & Roemer, 2004). The English version has Cronbach's α of 0.93 and test-retest reliability (ICC = 0.88) over four to eight weeks.

Then the scale translated by Wang et al. in 2007 (Wang L., 2007), The Chinese version has Cronbach's α of 0.87, and test-retest reliability (ICC = 0.87).

The Chinese version of 10-item Connor-Davidson Resilience Scale (CDRS)

The original version of the scale is a self-administered questionnaire with one single dimension(Campbell-Sills et al., 2006), which originated from the original 25-item one (Connor et al., 2003). It has 10 items with five response options (0 = never; 4 = almost always). The final score of the questionnaire is the sum of the responses of each item (range 0 - 40), where higher scores indicate higher resilience capacity. It was translated into Chinese in 2017 (Ye et al., 2017). The Chinese version of CD-RISC-10 retains its single dimension in the original English version. Cronbach's α for the entire scale was 0.88, and the test-retest was 0.73.

5. Data collection for qualitative phase

A preliminary interview outline will be developed based on a review of relevant literature and pre-tested with three patients before finalizing the interview guide. All interviews will be conducted by postgraduate nursing students with qualitative research experience. Participants will be briefed on the purpose and procedures of the interviews before conducting the prearranged interviews in the clinic. Each individual interview lasted 30-60 minutes; the sample will be considered saturated until no new themes arose. We will conduct interviews in the following aspects. (1) Background and emotional journey; (2) Emotional needs and support; (3) Strategies of emotional regulation and improving emotional granularity; (4) Attitudes toward ai-driven tools, perceived emotional appropriateness, cultural sensitivity, accessibility barriers, and suggestions for improvement. See appendix 2 for the interview guide.

6. Data analysis

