6.1 Quantitative data analysis

Statistical analyses will be conducted using IBM SPSS Statistics 27. Participant characteristics will be described as medians (quartile intervals) for continuous variables and numbers (percentages) for categorical variables. Group differences in emotional granularity, emotional coping, and resilience will be examined using one-way ANOVAs and independent samples t-tests. Pearson's bivariate correlations will assess associations among emotional granularity, emotional coping, and resilience. Confirmatory factor analysis (CFA) will be performed using IBM SPSS Amos 27.0 to validate the measurement models, with acceptable model fit indices defined as $\chi^2/df \leq 3$, GFI, AGFI, CFI > 0.90, and RMSEA < 0.06 (Awad et al., 2022). A simple

mediation model will test whether emotional regulation mediates the relationship between emotional granularity and resilience using bootstrapping (5,000 resamples) and bias-corrected confidence intervals (Igartua & Hayes, 2021). Missing data will be handled using multiple imputation, and two-sided $p < 0.05$ will be considered statistically significant.

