6.3 Data integration

Quantitative and qualitative data will be integrated using a sequential explanatory design. A comparison matrix will link quantitative findings with qualitative themes, enabling interpretation of how emotional granularity and emotional regulation relate to resilience. Discrepancies or unique insights will be discussed and interpreted in context, and final reports will present a synthesized perspective combining statistical evidence and participants' experiences.

7. Ethical Considerations

This study will comply with the Declaration of Helsinki. Ethical approval of the research protocol will be obtained from the Human Subjects Ethics Sub-Committee (HSESC) of the Hong Kong Polytechnic University and the ethics committee of the medical institutions in Suzhou. Informed consent will be obtained from each participant. The principles of voluntariness, non-maleficence, beneficence, and confidentiality will be emphasized throughout the research process.

For the quantitative phase, all survey data will be de-identified and stored on encrypted drives with access restricted to authorized research team members only. Hard copy documents, if any, will be stored in locked cabinets in secure offices. All information will remain confidential, and no identifying information will be disclosed in any reports, presentations, or publications. The data will be retained for five years after publication of the study findings, after which all personal identifiers and linked codebooks will be permanently destroyed, leaving only fully anonymized data for archival purposes.

For the qualitative phase, audio recordings will be collected only with participants' consent and anonymized during transcription. All transcripts and notes will be stored securely on password-protected, encrypted drives with access limited to authorized research team members. The data will be retained for five years after publication of the study findings, after which all personal identifiers and linked codebooks will be permanently destroyed, leaving only fully anonymized data for archival purposes.

All online patient information will be stored in encrypted format, and de-identification will be applied to patient text and voice data used for analysis.

8. Quality and Rigor

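### If more than one hospital recruits, hospital should be recorded and adjusted for: left out, it can bias the mediation estimates in either direction

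*Combined protocol and SAP*

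**What the plan says.** - **Sites.** Section 3 has patients "recruited consecutively from Chinese medical institutions in Suzhou, Jiangsu Province", and section 7 refers to "the ethics committee of the medical institutions in Suzhou". Both are plural and neither gives a number. Section 3 also has records searched "in accordance with the hospital's strict data security policies", in the singular.
- **Form.** Section 4 lists the general items: "The questionnaire includes age, sex, nationality, marital status, education, occupation, religious beliefs, monthly per capita household income, payment method of medical expenses", followed by clinical items. Neither this list nor the printed form in Appendix 1 has a hospital or site field. The only identifier is the inpatient number, which the form treats as the patient's unique number.
- **Model.** Section 6.1 states that a simple "mediation model will test whether emotional regulation mediates the relationship between emotional granularity and resilience using bootstrapping (5,000 resamples", with bias-corrected intervals. It names no covariate, hospital term, stratification or allowance for clustering. The planned t-tests and ANOVAs do not name hospital either.
- **Scales.** Under section 4, the regulation scale (DERS) measures difficulties, and a higher score on the resilience scale means more resilience.
- **Size.** Section 3 assumes standardized paths a = 0.5 and b = 0.4, says that "200 participants will reliably ensure at least 80% power", and allows 15% attrition to reach 236.

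**The concern.** All three constructs are self-reports, collected in one cross-sectional survey and analysed as one homogeneous sample. Hospitals may differ in stoma rate, stage, treatment, income mix or the way forms are completed. If such a difference moves two of the scales, patients pooled across hospitals show an association, or lose one, that does not exist within any hospital.

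What is at stake is the estimate and error rate of paths a and b, of the indirect effect, and of the Pearson correlations tested at the same 5% level. The problem may also be hard to repair later. The survey is described as anonymous, the data are de-identified, and no link from inpatient number to hospital is planned. If hospitals issue their own inpatient numbers, two patients could share one.

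**Working it through.** **1. The plan's own figures.** 200 / (1 - 0.15) = 235.3, rounded up to 236, which reproduces. Simulated power at N = 200 with a = 0.5 and b = 0.4 is about 1.00, so the claim of at least 80% is true. About 60 patients would already give 80%.

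**2. Inputs.** From the plan: N = 200, the two paths and two-sided 5%. Assumed, because the documents give no values: 2 to 5 equal hospitals, an ICC of 0.02 to 0.10, and hospital shifts that coincide fully across scales unless stated otherwise. The simulations used simpler tests and intervals than the planned bias-corrected bootstrap, so error rates are approximate.

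**3. Spurious path a.** With J hospitals, the expected between-hospital variance within the sample is f = ICC × (J - 1) / J. With no true effect and standardized scores, a fully shared shift gives a spurious path of about f.
- J = 2, ICC 0.10: 0.10 × 1/2 = 0.05 (simulated 0.051).
- J = 5, ICC 0.10: 0.10 × 4/5 = 0.08 (simulated 0.081).

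**4. Direction when the effect is real.** Under the study hypothesis, raw DERS scores give a = -0.5 and b = -0.4, with product +0.20. For a shift s = +1 (granularity and DERS move the same way) or s = -1 (opposite ways), a shift on the observed scores gives

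a(unadjusted) ≈ [(1 - ICC) × (-0.5) + s × f] / [(1 - ICC) + f].

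For J = 4 and ICC 0.10, f = 0.075:
- s = +1: (-0.45 + 0.075) / 0.975 = -0.385, weaker than the true -0.5.
- s = -1: (-0.45 - 0.075) / 0.975 = -0.538, stronger.

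Reverse-scoring DERS first changes the signs but not this result, because the shift reverses with the score.

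**5. Simulated results, hospital omitted, fully shared shifts.**

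| ICC | False positives, path a (2-4 hospitals) | False positives, indirect effect, no true paths (2-5 hospitals) | Estimate of a true 0.20, same-direction raw shift (2 or 4 hospitals) |
|---|---|---|---|
| 0.02 | 5-7% | 0.2-0.3% | 0.17-0.18 |
| 0.05 | 9-10% | 0.9-1.4% | 0.14-0.16 |
| 0.10 | 15-23% | 6.2-8.5% | 0.10-0.14 |

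- The path a column also applies to the granularity-regulation correlation: with no covariates the two tests are the same.
- If a = 0 but b is real, the indirect-effect test gives false positives of about 9% at ICC 0.05.
- A case-mix shift (worse regulation, lower granularity and resilience) moves a true 0.20 up to about 0.205-0.23 over the three ICCs.
- That upper figure depends on where the shift enters. If hospital acts on each equation in addition to what earlier scores carry forward, path a becomes 0.5 + f / (1 - ICC + f) in the hypothesised direction. For J = 5 and ICC 0.10 this is 0.5 + 0.08/0.98 = 0.582, and the mean indirect effect reaches 0.257-0.287 with 2 to 5 hospitals.
- If the hospital shifts on the scales are unrelated, there is no average bias, but path a false positives still reach about 10-12% at ICC 0.10.

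**6. With hospital indicators in both equations.** Path a false positives are 4-6%, the mean indirect effect is 0.197-0.202 against a true 0.20, and power stays at about 1.00.

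**The case against.** Four points can be made for the plan as written.

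- **Every driving input is assumed.** The documents give no number of hospitals, ICC or correlation of shifts. At ICC 0.02 the path a error rate is close to nominal. With one recruiting site, which the singular wording in section 3 leaves possible, the issue disappears. This stands and limits the weight of the point.
- **A reader might infer that shared hospital shifts always create or exaggerate the association.** The documents do not support that: because DERS scores difficulties, a common raw shift on all three scales hides the hypothesised effect.
- **A reader might infer that the planned mediation test does not hold its 5% level.** That is not established. With no true paths, the indirect-effect test stays below 5% except near ICC 0.10. It exceeds 5% at lower ICCs only in particular cases, such as a = 0 with a real b.
- **Administration is partly controlled.** Participants fill in the form themselves, assistants read items word for word only to those with reading difficulty, and section 8 requires standard procedures. The form also records stage, stoma, treatment, complications and income. But the model uses none of these, so case mix by hospital remains in the estimates.

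Staff might also trace the hospital from the inpatient number. That is possible, but it is not planned.

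**Conclusion.** The point holds in conditional form. If more than one hospital recruits, the plan neither records hospital nor allows for it, and paths a and b and the indirect effect can be biased in either direction. Under the assumed range (N = 200, 2 to 4 hospitals, ICC 0.02 to 0.10, fully shared shifts on the observed scores), path a error runs from about 5% to 23%, and a true indirect effect of 0.20 is estimated between about 0.10 and 0.23. The larger figures need both a high ICC and coinciding shifts, and at ICC 0.02 the harm is small. The documents do not show that hospitals differ, or that more than one will take part, and the sample size is not called into question. This is a cheap improvement, not a flaw that undermines the study.

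**What to change.** - State in section 3 how many institutions recruit, and reconcile the plural and singular wording.
- If there is more than one, add a site code to the Appendix 1 form, so that site plus inpatient number identifies the patient.
- In section 6.1, include hospital indicators in both mediation equations and resample within hospital in the bootstrap. Fixed indicators suit a handful of sites better than a random effect, which few sites cannot estimate reliably.
- Report the path estimates and the indirect effect with and without the adjustment.

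The cost is one form field and J - 1 degrees of freedom per equation (3 with four hospitals), with negligible loss of precision if hospitals do not differ. The targets of 200 analysed and 236 recruited do not change. The site code must be in place before the survey starts, since it may not be recoverable afterwards.
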